CA	Competent Authority
CCMO	Central Committee on Research Involving Human Subjects; in Dutch: Centrale Commissie Mensgebonden Onderzoek
CV	Curriculum Vitae
DSMB	Data Safety Monitoring Board
EU	European Union
GCP	Good Clinical Practice
GDPR	General Data Protection Regulation; in Dutch: Algemene Verordening Gegevensbescherming (AVG)
HA	Hyperandrogenism
IC	Informed Consent
METC	Medical research ethics committee (MREC); in Dutch: medisch-ethische toetsingscommissie (METC)
OD	Ovarian Dysfunction
PCOM	Polycystic ovarian morphology ovarian dysfunction (OD)
(S)AE	(Serious) Adverse Event
Sponsor	The sponsor is the party that commissions the organisation or performance of the research, for example a pharmaceutical company, academic hospital, scientific organisation, or investigator. A party that provides funding for a study but does not commission it is not regarded as the sponsor, but referred to as a subsidising party.
UAVG	Dutch Act on Implementation of the General Data Protection Regulation; in Dutch: Uitvoeringswet AVG
WMO	Medical Research Involving Human Subjects Act; in Dutch: Wet Medisch-wetenschappelijk Onderzoek met Mensen

SUMMARY

Rationale:

Polycystic ovary syndrome (PCOS) is an endocrine disorder that affects up to 10% of reproductive-aged women worldwide. According to the Rotterdam criteria the syndrome is diagnosed based on two of the following three criteria: ovarian dysfunction (OD), hyperandrogenism (HA) (clinical or biochemical), and/or polycystic ovarian morphology (PCOM) (1) and there are four different PCOS phenotypes based on the features (2).

In PCOS women, not only is infertility a concern but the syndrome is also associated with obesity, insulin resistance, type 2 diabetes mellitus, metabolic syndrome, and cardiovascular risk factors (3).

Various factors have been reported to contribute to the pathophysiology of PCOS, but due to the heterogeneity of the syndrome, the pathophysiology remains unclear. However, studies emerged on the crucial role of the gut microbiome in human health. Recent studies confirmed that the gut microbiome is altered in women with PCOS compared to healthy women (4-7), and some of these alterations have been linked to the clinical markers of PCOS (4, 5). Different PCOS phenotypes may show different gut microbiome features due to the heterogeneity of this syndrome, which makes it hard to detect the significant changes in the gut microbiome. Age, obesity, androgen status, and insulin resistance or glucose intolerance should all be taken into account while studying the gut microbiome of PCOS patients.

Even though studies have proven that PCOS patients have an altered gut microbiome, the characteristics of microbiome diversity and the specific types of gut bacteria have remained inconsistent. Studies reported on specific alterations of alpha and beta diversity in PCOS patients. Although some studies have shown that decreased alpha diversity and altered beta diversity were associated with PCOS (4, 5, 8), many studies have reported that microbial diversity remained unchanged (9-11).

Studies have investigated correlations between the clinical features of PCOS and the gut microbiome. Features of PCOS such as hyperandrogenism, hirsutism, insulin resistance, and obesity can all have an impact on the gut microbiome to some extent. The decrease in α -diversity has been linked to total testosterone levels and hirsutism (9, 12), and changes in β -diversity were also correlated with hyperandrogenism (5). Also, some even suggested that the hyperandrogenism seen in the PCOS rodent model may affect the gut microbiome independently of diet (13). The role of metabolic factors, such as obesity and insulin resistance, in the PCOS patient's gut microbiome, remains unclear. Although another study showed that obesity itself is linked to a decrease in gut microbial diversity (12), most studies on the gut microbiome in PCOS have included BMI-matched controls to exclude the

influence of body weight. In another study, BMI was found to positively correlate with three bacterial species, while waist-to-hip ratio and fat mass were also found to significantly correlate with the levels of multiple species (9, 12).

While the etiology of the microbiome-mediated disease is yet unknown, one possible pathway is microbial metabolism. Using metabolomics technology to identify metabolites that constitute chemical fingerprints of several metabolic pathways relevant for the pathogenesis of PCOS. While PCOS affects metabolites from various metabolic pathways, this primarily includes abnormalities in the metabolism of lipids, steroid hormones, carbohydrates, and amino acids. Identifying disrupted pathways enables PCOS-specific molecules that could be used as biomarkers and future metabolomic research targets.

Fewer studies are available investigating the relationship between PCOS and the vaginal microbiome, due to challenges in translating the vaginal microbiome of rodent models to humans. However, more consistent results were observed for the vaginal microbiome of PCOS patients (14, 15). The reason could be that the vaginal microbiome has lesser biomass and biodiversity than the gut, which makes it easier to get affected by PCOS.

As far as we are aware, there are no studies investigating the vaginal microbiota and its relation with sex hormone concentrations and PCOS phenotypical, diagnostic, and metabolic characteristics. This study aims to get a better understanding of the relationship between PCOS phenotypical, diagnostic, and metabolic characteristics (hirsutism, hyperandrogenism, ovarian dysfunction, polycystic ovary) and the gut- or vaginal microbiome in overweight/obese and lean patients. Hopefully, this may lead to a better understanding of the role of this microbiota in the pathogenesis of PCOS and future perspectives on treatment options.

The hypothesis is that PCOS patients have a less diverse microbiome in comparison with non-PCOS patients. Obese patients with PCOS will have a more severe dysbiosis of the gut microbiome than lean patients with PCOS.

Objective:

To analyse, characterise and determine the gut- and vaginal microbiome and its association with PCOS.

Main objectives

- To analyse whether there is an association between the gut microbiome and PCOS as such and its diagnostic and metabolic characteristics.

Secondary objectives

- To analyse whether there is an association between the *vaginal* microbiome and PCOS as such and its diagnostic and metabolic characteristics.
- To analyse whether there is a correlation between the composition of the gut- and vaginal microbiome in PCOS patients
- To analyse the difference in gut- and vaginal microbiome composition between overweight/obese and lean (with/without PCOS).
- To analyse potential metabolic profiles characterizing different phenotypes of PCOS

Study design: A prospective observational case-control study, conducted at the Department of Obstetrics and Gynecology (Division of Reproductive Medicine) at the Erasmus University Medical Center Rotterdam

Study population: Patients with PCOS diagnosed based on the Rotterdam criteria must be Caucasian women, aged 18 - 45 years old (premenopausal), either overweight or obese (BMI>25) or lean (BMI18-25).

Main study parameters/endpoints:

The main parameter of this study is the differences in community structure (presence or absence of bacteria, alpha, and beta diversity) of the gut microbiome between PCOS patients and controls.

Secondary study parameters: 1. Differences in community structure (presence or absence of bacteria, alpha, and beta diversity) in the *vaginal* microbiome between PCOS patients and controls. 2. The differences and similarities between the vaginal- and gut microbiome composition in PCOS patients 3. The differences and similarities between the vaginal- and gut microbiome composition between overweight/obese and lean patients (with/without PCOS). 4. Metabolic profiles from different phenotypes of PCOS

Nature and extent of the burden and risks associated with participation, benefit, and group relatedness:

For all participants, the risks involve primarily the burden of participating in a study, which in the current study proposal means 1 additional hospital visit and assessments. Women from the study group have already undergone the regular physical examination (transvaginal ultrasound) and laboratory tests for the standard outpatient clinic for COLA (Cycle disorders, Oligomenorrhea and Amenorrhea) screening. Patients will be asked to collect a stool sample at home and bring or send this to the hospital. A vaginal sample will be obtained by a physician without using a speculum. The risks of participation are considered to be minor and there are no obvious risks associated with participation in the study. The assessment and determination of relevant gut and vaginal microbiome may lead to a better understanding of

the pathophysiology of PCOS and might provide future intervention strategies eventually leading to new therapeutic options reducing the risk of metabolic risk factors. Therefore, this project will have an impact on research, individual clinical care as well as on future medical health care costs.

1. INTRODUCTION AND RATIONALE

Polycystic ovary syndrome (PCOS) is an endocrine disorder that affects up to 10% of reproductive-aged women worldwide. According to the Rotterdam criteria the syndrome is diagnosed based on two of the following three criteria (2): ovarian dysfunction (OD), hyperandrogenism (HA) (clinical or biochemical), and/or polycystic ovarian morphology (PCOM) (1). PCOS phenotypes are currently classified as phenotype-A (HA+ OD+ PCOM), phenotype-B (HA+OD), and phenotype-C (HA+PCOM). Phenotype-A or full-blown phenotype is present in half of the patients who present in the clinic. See Supplementary Table 1.

In PCOS women, not only is infertility a concern, but the syndrome is also associated with obesity, insulin resistance, type 2 diabetes mellitus, metabolic syndrome, and cardiovascular risk factors (3). Various factors have been reported to contribute to the pathophysiology of PCOS, such as lifestyle, metabolic status, and genetic and epigenetic variants. However, studies emerged on the crucial role of the gut microbiome in human health. Recent studies confirmed that the gut microbiome is altered in women with PCOS (4-6). The gut microbiome composition of PCOS patients is altered compared to healthy women and some of these alterations have been linked to the clinical markers of PCOS (4, 5). PCOS patients seem to have a leaky gut: the gut bacteria change the intestinal lining, resulting in the release of bacterial endotoxins into the bloodstream. This could activate pro-inflammatory cytokines, promoting insulin resistance, hyperandrogenism, and fat storage, all of which are linked to PCOS (16).

Even though studies have proven that PCOS patients have an altered gut microbiome, the characteristics of microbiome diversity and the specific types of gut bacteria have remained inconsistent. Studies reported on specific alterations of alpha and beta diversity in PCOS patients. Alpha diversity refers to the number of different taxa within a specific community; it indicates the richness of the gut microbiome. Beta diversity is a measure of how comparable the gut microbiome is between healthy people and PCOS patients. Although some studies have shown that decreased alpha diversity and altered beta diversity were associated with PCOS (4, 5, 8), many studies have reported that microbial diversity remained unchanged (9-11). Of note, a recent study with more than 300 subjects did not find microbial diversity in PCOS patients compared to healthy patients. Although, this was a population-based cohort study, and subjects were asked retrospectively whether they had oligomenorrhea, hirsutism or were diagnosed with PCOM. Several other reasons could have led to an unchanged microbial diversity and inconsistent outcomes, such as small sample size, and differences in sequencing techniques and analytical methods.

Unlike gut microbial diversity, most human studies have found differences in taxa between healthy women and PCOS patients. The phyla *Bacteroidetes*, *Firmicutes*, and *Tenericutes*,

as well as the families *Bacteroidaceae*, *Ruminococcaceae*, *Lachnospiraceae*, *Prevotellaceae*, and *Streptococcaceae*, are mostly represented. In many studies, significant changes in *Bacteroides* abundance were discovered (6, 7, 10, 17, 18). In addition, a metagenomic analysis revealed the existence of specific species of *Bacteroides spp.* in PCOS patients. The most typical aspect of the gut microbiome in patients with PCOS, according to Qi et al., is an increase in the abundance of *Bacteroides vulgatus* (6). More notably, administration of *B. vulgatus* mimics PCOS characteristics in mice (6). Additionally, *Bacteroides fragilis* was shown to be more abundant in another metagenomic study, and its abundance was positively linked with luteinizing hormone (LH) and antimullerian hormone levels (AMH) (17). According to these studies, *Bacteroides spp.* plays an important role in PCOS patients. More research is needed to compare the pathogenic role of several species of *Bacteroides spp.*

Studies have investigated on correlations between the clinical features of PCOS and the gut microbiome. Features of PCOS such as hyperandrogenism, hirsutism, insulin resistance and obesity can all have an impact on the gut microbiome to some extent. The decrease in α -diversity has been linked to total testosterone levels and hirsutism (9, 12), and changes in β -diversity was also correlated with hyperandrogenism (5). Also, some even suggested that the hyperandrogenism seen in the PCOS rodent model may affect the gut microbiome independently of diet (13). The role of metabolic factors, such as obesity and insulin resistance, in the PCOS patient's gut microbiome remains unclear. Although another study showed that obesity itself is linked to a decrease in gut microbial diversity (12), most studies on the gut microbiome in PCOS have included BMI-matched controls to exclude the influence of body weight. In another study, BMI showed positive correlations with three bacterial species and waist-to-hip, ratio and fat mass was also correlated with several species levels (9, 12).

While the etiology of microbiome-mediated disease is yet unknown, one possible pathway is microbial metabolism. Using metabolomics technology in order to identify metabolites that constitute chemical fingerprints of several metabolic pathways relevant for the pathogenesis of PCOS. Hyperandrogenism appears to be the major pathological component in the etiology of PCOS, according to a rodent study. In this work, eliminating the gut microbiota of DHEA-treated rats did not prevent PCOS phenotypes, however transplanting microbiota from androgen-treated rats into pseudo germ-free animals caused hepatic glucolipid metabolic disruptions and reproductive hormone imbalance (19).

Human studies have shown that levels of metabolites from different biochemical pathways are altered in women with PCOS, but abnormalities in hormone and lipid metabolism were mainly involved in the onset of PCOS (20). Also, metabolites connected to amino acids as well as energy metabolism such as citric acid cycle appear to be the most common. Glycerophospholipid metabolism was shown to be down-regulated in PCOS, while glucose metabolism was found to be up-regulated. Zhao et al. found that in PCOS, all of the measured fatty acids are up-regulated when compared to control patients (21). According to Zou et al., certain carbohydrates and fatty acid metabolites are up-regulated in PCOS compared to controls (22). Identifying disrupted pathways enables of PCOS-specific molecules that could be used as biomarkers and future metabolomic research targets. Finding relevant biochemical indicators may help in early diagnosis and future targeted pharmacological therapies.

Fewer studies are available investigating the relationship between PCOS and the vaginal microbiome, due to challenges in translating the vaginal microbiome of rodent models to humans. However, a recent study found lower abundances of *Lactobacillus spp.* and elevated levels of *Gardnerella*, *Prevotella*, and *Mycoplasma* (15). In addition, the authors found highly comparative microbiome composition in vaginal and cervical canal samples in the same patient. In correspondence to another case-control study, they found that women with PCOS have higher alpha diversity, lower abundances of *Lactobacillus crispatus*, and higher abundances of *Mycoplasma* and *Prevotella* (14), after adjusting for BMI. These studies suggested a more consistent conclusion in the vaginal microbiome of PCOS patients. The reason could be that the vaginal microbiome has lesser biomass and biodiversity than the gut, which makes it easier to get affected by PCOS.

As far as we are aware, there are no studies investigating the vaginal microbiota and its relation with sex hormone concentrations and PCOS phenotypical, diagnostic and metabolic characteristics. This study aims to get a better understanding of the relationship between PCOS phenotypical, diagnostic and metabolic characteristics (hirsutism, hyperandrogenism, ovarian dysfunction, polycystic ovary) and the gut- or vaginal microbiome in overweight/obese and lean patients. Hopefully, this may lead to a better understanding of the role of these microbiota in the pathogenesis of PCOS and future perspectives on treatment options.

The hypothesis is that PCOS patients have a less diverse microbiome in comparison with non-PCOS patients. Obese patients with PCOS will have a more severe dysbiosis of the gut microbiome than lean patients with or without PCOS.

2. OBJECTIVES

To analyse, characterise and determine the gut- and vaginal microbiome and its association with PCOS clinical phenotypes.

Main objectives

- To analyse whether there is an association between the gut microbiome and PCOS as such and its diagnostic and metabolic characteristics.

Secondary objectives

- To analyse whether there is an association between the vaginal microbiome and PCOS as such and its diagnostic and metabolic characteristics.
- To analyse whether there is a correlation between gut- and vaginal microbiome in PCOS patients and controls
- To analyse the difference in gut- and vaginal microbiome composition between obese and lean (with/without PCOS).
- To analyse potential metabolic profiles characterizing different phenotypes of PCOS

3. STUDY DESIGN

This is a prospective observational case-control study, conducted at the department of Obstetrics and Gynecology (Division of Reproductive Medicine) at the Erasmus University Medical Center Rotterdam. In this study changes of the gut- and vaginal microbiome will be analysed in correlation with PCOS phenotypes.

Patients: women diagnosed by the division of Reproductive Medicine with PCOS in West- or Central Europe*

Sample size: n=50 PCOS overweight/obese and n=50 PCOS lean patients

Moments of inclusion: after PCOS diagnosis/ COLA screening (Cycle disorders, Oligomenorrhea and Amenorrhea screening)

Controls: n=50 overweight/obese and n=50 lean non-PCOS healthy women

Test sample: vaginal swab, stool sample and blood sample

Study period: 1-11-2022 – 1-12-2024

* The diet is strongly associated with the gut microbiome. The reason to only include women from Western and Central Europe, is because these women have a different diet compared to women from Asian, Mediterranean and African countries (recently reviewed in:(23)) . We want to include women who have a Western diet. In addition, the vaginal microbiome is structurally different across ethnicities (24). To avoid getting too small groups in sub-analyses based on ethnicity or diet, we chose to include patients from Western and Central Europe.

4. STUDY POPULATION

4.1 Population (base)

Patients who have had COLA screening at the outpatient clinic of Reproductive Medicine.

Study group: overweight/obese women (BMI>25) and lean women BMI (18-25) with PCOS

Control group: overweight/obese women and lean women without PCOS.

4.2 Inclusion criteria

In order to be eligible to participate in this study, a subject must meet all of the following criteria:

- Age 18-45years (premenopausal)
- Caucasian
- Willing to provide vaginal swab and stool sample
- Willing to provide informed consent
- Sufficient command of the Dutch language
- Diagnosed with PCOS at Erasmus MC using the Rotterdam criteria 2003 (2) (see also H.15 Supplementary 1)

4.3 Exclusion criteria

A potential subject who meets any of the following criteria will be excluded from participation in this study:

- BMI <18
- Smoking
- Diabetes Mellitus or use of insulin sensitizer
- Chronic and acute infection diseases
- Endometriosis (American Fertility Score (AFS) III/IV)
- Elevated prolactin levels, thyroid disease, Cushing disease or gastro-intestinal disease
- The use of hormonal contraceptives, other steroid hormones in last 3 months
- Use of antibiotics, probiotics or laxatives in the last 3 months

Control group:

- o After a COLA screening, subjects who have not been diagnosed with PCOS and have a regular menstrual cycle without hyperandrogenism or PCOM will have their dossiers individually evaluated to see whether they can participate in the control group.
 - o COLA screening volunteers who have already agreed to be approached for any future studies, will receive the PIF and be asked to participate in this study. These candidates are healthy and have a regular menstrual cycle.
 - o Online advertisement will be published to recruit volunteers.
- Inclusion criteria control group:
 - o Age 18-45years (premenopausal)
 - o Caucasian
 - o Willing to provide vaginal and stool sample
 - o Willing to provide informed consent
 - o Regular menstrual cycle (25-35days)
 - o Sufficient command of the Dutch language
 - o No history of diagnosed PCOS and do not meet any of the Rotterdam criteria.
- Exclusion criteria: see above.

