8.3 Study procedures

Patients are eligible for the study after they are diagnosed with PCOS at the regular COLA screening. The abbreviation COLA stands for: Cycle disorders, Oligomenorrhea and Amenorrhea. During the regular COLA screening visit, patients will undergo a physical examination, including a transvaginal ultrasound. Three to four weeks after the COLA screening patients will receive their COLA screening results. Patients who are diagnosed with PCOS and are eligible for the study will be informed about the details of the study. Patients will receive a patient information leaflet with the informed consent form, together with the contact information of the clinical coordinator in case they might have any remaining questions.

The main investigator will contact them by phone 1 week after their appointment for their COLA screening result and ask if they are interested in participating in the study. If the patient agrees to participate, the material for stool sample collection will be sent to her. Patients will be instructed to collect the stool sample after signing the informed consent (preferably on the day of the second appointment, but no more than 2 days before) On the day of the second appointment, the researcher will sign the informed consent and provide a copy to the patient. A vaginal swab will be obtained by the physician and the stool sample will be handed in by the patient.

Vaginal samples and blood samples will be collected in the non-menstrual period during the appointment. Patients will be asked to fill in an online Food Frequency Questionnaire (max 45min).

Also, PCOS patients in the COLA database who are eligible will be approached to participate in this study. They will be contacted by phone, and if they are interested in participation, a PIF will be sent to their home address.

Participants in the control group will be informed by the main investigator. When they meet the inclusion criteria and they decide to participate in the study, the same COLA screening will be conducted, in combination with this study protocol.

COLA screening volunteers who have already agreed to be approached for any future studies, will receive the PIF and be asked to participate in this study. These candidates are healthy and have a regular menstrual cycle.

Online advertisement will be published to recruit volunteers.

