11.2 Recruitment and consent

Women who are eligible for the study will be informed by the clinician about the the GuVa PCOS study and when the patient is interested in participation, the main investigator will contact the patient. The main investigator will inform the patient. about the voluntary nature of their participation as well as by means of the information leaflet and informed consent form. Full comprehensive information will be given to all patients according to the regulations of the competent authorities that need to approve the clinical study. Participants in the control group will be recruited via online advertisement and via the outpatient clinic of Reproductive medicine.

Informed consent:

The study will be performed according to written informed consent procedures and this study protocol that are approved by local and/or national ethics committees. The informed consent procedures ensure personal data protection and confidentiality. Data will be coded, i.e. information will not be directly traceable to an individual person.

Patients who signed the informed consent, agree on sharing unexpected findings with the specialist or general practitioner. Patients who do not want their physician and or general practitioner to be informed about the following, cannot participate in the study.

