12. ADMINISTRATIVE ASPECTS, MONITORING ,AND PUBLICATION

12.1 Handling and storage of data and documents

Each subject will be assigned a study number. Data on microbiome composition will be stored anonymously and coded on basis of that study number. Only the coordinating investigators, project leader, and the principal investigator(s) will have access to patient identifying data and their respective study numbers. This is according to the EU General Data Protection Regulation and the Dutch Act on Implementation of the General Data Protection Regulation.

Storage of samples

Vaginal and stool samples will be frozen at -80°C and stored up to a maximum of 25 years.

Storage of data

Every patient will have to sign an informed consent form. All data will be stored and handled in the same way and according to the same rules and regulations as other patient-related data at the Erasmus MC. It will be stored as files on a separate research storage platform. Access will be limited to authorized study personnel. Should data transfer to other parties be necessary for testing or validation purposes, we will code the datasets and remove all personal data before the transfer. Data and information about the patient will be extracted from the clinical file. The signed consent forms must accompany the rectal and vaginal swab samples.

Data extracted from the clinical file are:

- Age
- Body Mass Index (BMI)
- Ethnicity
- Hirsutism or not (and Modified Ferriman Gallwey score)
- PCOM (polycystic ovarian morphology) or not
- Amenorrhea or oligomenorrhea
- Smoking / non-smoking
- Alcohol consumption
- Previous treatments for fertility
- Gynaecological history
- General health status and diseases
- Operations before treatment

- Menstrual cycle
- Previous use of antibiotics (estimated dates)
- Use of hormonal contraceptives

Data will be stored in a databank file in the Erasmus MC using Castor. Data will be further analyzed using analyzing and statistical software (e.g. R). The originally informed consent will be archived. Data sets used for analysis will be stored along with data analysis output and syntax files to facilitate control measures. These sets of data and files will be stored together with the versions of scientific publications reporting the findings of the study for an unlimited time.

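### Recent intercourse, non-hormonal contraception and vaginal products are neither timed nor listed for recording, so the secondary vaginal comparison cannot be checked or adjusted for them

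*Protocol*

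**What the plan says.** Section 4.3 of the protocol excludes "Use of antibiotics, probiotics or laxatives in the last 3 months", "The use of hormonal contraceptives, other steroid hormones in last 3 months" and "Chronic and acute infection diseases". The antibiotic, probiotic and hormone rules name no route. The control group has the same list: "Exclusion criteria: see above".

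For the swab, section 8.3 sets one timing condition: "Vaginal samples and blood samples will be collected in the non-menstrual period during the appointment". It gives no other pre-swab instruction.

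Section 12.1 lists the items taken from the medical record. These include "Gynaecological history", earlier fertility treatment, the menstrual cycle, dated antibiotic use and "Use of hormonal contraceptives".

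Cases are women diagnosed with PCOS at the clinic's COLA screening, or eligible women from the COLA database (sections 3, 4.1 and 8.3). On controls, section 11.2 says: "Participants in the control group will be recruited via online advertisement and via the outpatient clinic of Reproductive medicine". Sections 4.3 and 8.3 add earlier COLA volunteers.

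Section 8.1.2 lists the vaginal comparison of PCOS patients with controls first among the secondary endpoints. For the vaginal site, section 10.2 names PCOS-related variables such as BMI, androgens and insulin, and no local exposure.

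**The concern.** A case-control comparison of the vaginal microbiome is open to any exposure that acts on the vagina and differs between the groups. Several such exposures are handled by exclusion. Four are not: recent intercourse, non-hormonal contraception, vaginal hygiene products, and vaginal medication other than antibiotics, such as antifungals. Part of the control group is recruited by a route that the cases do not share, so imbalance is possible.

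The protocol treats the gut differently. It limits eligibility by region of origin because of diet (section 3), and it gives participants a food frequency questionnaire (section 8.3) that enters the analysis (section 10.2). No comparable questionnaire serves the vaginal site.

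The gap lies in data collection. A statistical analysis plan can add covariates only if they were recorded, and recent exposures that are not asked about at sampling cannot be reliably reconstructed later. At stake is whether a vaginal difference, or its absence, can be attributed to PCOS.

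**Working it through.** **Step 1: which exposures are covered.**

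| Exposure | Excluded (4.3) | Timed (8.3) | Listed for recording (12.1) |
|---|---|---|---|
| Antibiotics, any route | yes, 3 months | – | yes, with dates |
| Probiotics, any route | yes, 3 months | – | no |
| Hormonal contraceptives, any route | yes, 3 months | – | yes |
| Other steroid hormones, any route | yes, 3 months | – | no |
| Infections | yes, in general terms | – | only through general health items |
| Menstruation | – | yes | menstrual cycle |
| Recent intercourse | no | no | no |
| Barrier method or non-hormonal intrauterine device | no | no | no |
| Vaginal hygiene products | no | no | no |
| Non-antibiotic vaginal medication | no | no | no |

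The last four rows are the gap. The gynaecological history item is generic and does not secure dated recent exposures.

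**Step 2: ultrasound and swab (section 8.3).** Newly diagnosed cases have the transvaginal ultrasound at COLA screening. Results follow three to four weeks later, the telephone call comes one week after that, and the swab is taken at a second appointment. The interval is therefore at least about 3 + 1 = 4 weeks. Controls have the same screening combined with the study procedures, and the order of ultrasound and swab is not stated. A swab shortly after an ultrasound is thus possible in controls and not in newly diagnosed cases.

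**Step 3: how large a bias could matter.** The plan gives no figure to reproduce: section 4.4 states no effect size, SD or power. From the documents come 100 women per group (sections 3 and 4.4) and a two-sided 5% level (section 10.2). The gap in exposure prevalence and the shift in diversity are assumptions.

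- SE of a standardised mean difference = √(2/100) = 0.141 SD.
- Difference detectable with 80% power = (1.960 + 0.842) × 0.141 = 0.40 SD.
- Bias b = prevalence gap × shift in SD.
- Rejection rate with no PCOS effect = Φ(b/SE − 1.96) + Φ(−b/SE − 1.96).

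| Prevalence gap | Shift 0.3 SD: bias, error rate | Shift 0.5 SD: bias, error rate |
|---|---|---|
| 10 points | 0.03, 5.5% | 0.05, 6.4% |
| 20 points | 0.06, 7.1% | 0.10, 10.9% |
| 30 points | 0.09, 9.8% | 0.15, 18.6% |
| 40 points | 0.12, 13.6% | 0.20, 29.3% |

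The gap matters only when the imbalance and the shift are both sizeable.

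**The case against.** A reader might infer that the exclusion list protects only the gut and that nothing relevant to the vagina is controlled or recorded. The documents do not support that. Only laxatives and gastro-intestinal disease are specific to the gut. The antibiotic, probiotic and hormone rules have no route limit and so reach vaginal use and hormonal intrauterine devices. Infections are excluded, swabs are non-menstrual, and section 12.1 takes gynaecological history and fertility treatment from the record.

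A reader might also infer that cases are trying to conceive while controls are not, so that the comparison mainly measures that. No section says so. COLA screening is for cycle disorders, the remark about infertility in section 1 describes the syndrome, and some controls come from the same clinic.

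The list in section 12.1 covers extraction from the clinical file only. The food questionnaire and the laboratory panel are not on it, so absence from it does not prove that a question is never asked. Model covariates may also be left to an analysis plan that is not shown.

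These arguments narrow the point considerably. What stands is that the protocol nowhere provides for collecting the four remaining exposures, and a later analysis plan cannot supply data that were not collected.

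**Conclusion.** The point holds in a limited form. Recent intercourse, non-hormonal contraception, vaginal hygiene products and non-antibiotic vaginal medication are neither timed nor listed for recording. An imbalance in them between cases and controls could therefore be neither seen nor adjusted for in the vaginal comparison. That endpoint is secondary, and the primary gut comparison is not affected.

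The size and direction of any bias are unknown. The range of about 6% to 29% rests on an assumed shift of 0.5 SD and gaps of 10 to 40 percentage points; at 0.3 SD it is 5.5% to 13.6%. A more extreme pairing gives more: a 50-point gap with a 0.5 SD shift is a bias of 0.25 SD and an error rate of 42.4%. Nothing in the protocol supports those inputs, so that figure should not be read as an estimate. Severity is optional to low.

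**What to change.** At the sampling visit, ask cases and controls the same short questions: the date of last unprotected intercourse, the current non-hormonal contraceptive method, and recent vaginal products or medication. Add these items to the data list in section 12.1. Report the vaginal PCOS v control model with and without these variables.

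In section 8.3, state the order of vaginal swab and transvaginal ultrasound for controls, so that the swab is not taken just after an ultrasound in one group only.

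No new exclusion or abstinence window is needed. The cost is a few minutes per participant and one added sensitivity analysis.
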